## **2. To investigate the prognostic and predictive ability of peripheral blood BRAFV600 mutational testing in patients with Stage II or resectable Stage III melanoma.**

The investigation of the prognostic and predictive ability of the assay will be based on the cohort of patients with Stage II and resected Stage III disease. Some of these patients will have a tissue-based BRAF assessment and a pre-treatment blood-based BRAF assay, and some of the patients will have the blood-based assay only.

We would expect that 50% of the cohort would have BRAF-mutated disease and that 90% of those patients will have follow-up data from which to assess the predictive ability of the assay. This results in a sample of size 50. BRAF status will be classified as positive or negative based on the post-resection, blood-based assay, and where applicable, for the tissue-based assessment.

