### 1.2 Primary Objectives

To determine the sensitivity and specificity of peripheral blood BRAFV600 mutation detection in patients with melanoma, we will analyze samples from two distinct cohorts of patients: 1) Patients with advanced melanoma; and 2) Patients with resected, Stage II or Stage III disease. A total of 110 patients in each cohort will be recruited to participate. Peripheral blood lymphocytes (PBL) and serum will be isolated from blood. RNA will be isolated from tissue and PBL/serum and BRAFV600 analysis will be performed. Patients will be identified as being either positive or negative for the BRAFV600 mutation based on the results of the tissue testing. The tumor tissue (either primary tumor or nodal/systemic metastasis) from each patient with advanced disease, or from all patients with Stage II or resectable Stage III disease with adequate tissue, will be analyzed in a CLIA-approved laboratory for BRAFV600 sequencing analysis, either at the MGH TRL or at Clariant Laboratories using the FDA-approved Cobas® test. The results of the tissue-based and peripheral blood test will be compared and percent concordance will be determined.

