
Obuchowski NA. Sample size calculations in studies of test accuracy. *Stat Methods in Medical Res* 1998; 7: 371-392.

	0.90	0.95	0.95	(0.87 to 0.98)
0.6	0.80	0.90	0.92	(0.85 to 0.96)
	0.90	0.95	0.96	(0.90 to 0.99)

The cohort of patients with Stage II and resectable Stage III melanoma is an exploratory cohort. We cannot predict the sensitivity and specificity of the assay in patients with Stage II or resected Stage III disease. In addition, only patients in this cohort with T4 disease or macrometastatic lymph nodes will have adequate tissue for assessment. However, we believe it is important to include this cohort since the ability to detect BRAF in this patient population may provide a basis for proposing further studies correlating BRAF detection with disease recurrence. The sensitivity and specificity of the assay will be calculated and presented with 90% joint confidence regions. Based upon a cohort size of 110 patients, the joint confidence regions for the sensitivity and specificity will be no wider than  $\pm 0.13$ .

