### Prognostic Ability of the Assay

Baseline assay results will be categorized as positive or negative and also be described on a continuous scale. The proportion of patients with a positive baseline assay will be presented with a 90% exact binomial confidence interval. Based on a cohort size of 50, the confidence interval will be no wider than 0.25. Confidence intervals will also be presented for the subgroups of patients with intermediate- or high-risk disease. We will also summarize continuous baseline assay levels using descriptive statistics for the complete cohort and according to subgroups.

Preliminary assessments of prognostic ability will be conducted using Kaplan-Meier (K-M) product-limit estimates for relapse or survival and stratified log-rank tests. K-M estimates will be stratified by AJCC stage and assay results to explore assay performance across different prognostic groups. Relapse-free survival and overall survival estimates at pre-specified time points will be presented with 90% confidence intervals estimated using log(-log(survival)) methodology. A secondary analysis will be conducted in the cohort with blood- and tissue-based assessments according to the four groups defined by their combined positive/negative status to look for differences in prognosis.

The relative effect of the blood-based assay with respect to relapse or survival will be estimated using Cox regression models. Since the AJCC staging incorporates prognostic factors such as number of involved nodes, tumor burden, ulceration, and tumor thickness, the Cox models will be stratified by AJCC stage to allow for differences in the baseline hazard of relapse or death. Models will include as covariates age, site of the primary melanoma, sex, and baseline serum LDH in addition to the blood-assay results. We will use aggregated data for the primary models; secondary models will be fit separately for the intermediate- and higher-risk cohorts. Hazard ratios for the assay will be presented with 90% confidence intervals.

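### The Stage II/III prognostic and predictive analyses are sized on 50 BRAF-mutated patients, a set the design cannot identify independently of the blood assay; the analysis set and its n need to be stated

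*Combined protocol and SAP*

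**What the plan says.** Section 1.2 sets the cohort size: "A total of 110 patients in each cohort will be recruited to participate". For the Stage II/resected Stage III cohort, section 9.1, Secondary Objective 2, sizes the analysis as follows: "We would expect that 50% of the cohort would have BRAF-mutated disease and that 90% of those patients will have follow-up data", and concludes "This results in a sample of size 50".

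The same subsection notes that "some of the patients will have the blood-based assay only" and gives the status rule: "BRAF status will be classified as positive or negative based on the post-resection, blood-based assay, and where applicable, for the tissue-based assessment". Under the primary objective in section 9.1, the plan says that "only patients in this cohort with T4 disease or macrometastatic lymph nodes will have adequate tissue for assessment". Section 1.3, item 2, names a slightly wider group for tissue testing, adding satellite and in-transit lesions, but it also leaves the remaining patients without a planned tissue result.

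The 50 is then carried forward. Under Prognostic Ability of the Assay, the interval for the proportion with a positive baseline assay is sized on it: "Based on a cohort size of 50, the confidence interval will be no wider than 0.25". Under Predictive Ability of the Assay, the three-month signed-rank test starts from 50 patients and keeps 45. Kaplan-Meier, stratified log-rank and Cox analyses compare outcome by blood-assay result. A four-group analysis by blood and tissue status is secondary and limited to patients who have both.

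**The concern.** The sample size counts mutation carriers, but in this cohort many carriers cannot be recognised except through the assay being evaluated. Secondary Objective 1 uses the same arithmetic for the advanced cohort, but there it ties the 50 to mutation confirmed in tissue. Secondary Objective 2 has no such anchor.

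The plan therefore does not fix who is in the denominator of the positivity rate, or who forms the assay-negative group in the survival comparisons. Depending on how the set is assembled, the same data give different positivity rates, different precision and a hazard ratio with a different meaning. Section 9.1 says this cohort may provide a basis for further studies correlating BRAF detection with recurrence, so an unclear denominator would carry into their planning.

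**Working it through.** **Inputs from the documents.** Cohort 110 (section 1.2); 50% mutated and 90% of those with follow-up (section 9.1, Secondary Objective 2); exact 90% binomial interval with stated width at most 0.25 (Prognostic Ability of the Assay); about 11% progressed by three months (Predictive Ability of the Assay).

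**Assumptions.** The documents give neither the share of patients with tissue, t, nor the share of mutated patients who are blood-positive after resection, q. I take t = 0.3 to 0.7 and q = 0.2 to 0.5, with t = 0.5 and q = 0.3 as the example. I also assume perfect specificity, the same mutation prevalence with and without tissue, and 90% follow-up in everyone.

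**Step 1: the plan's own figures reproduce.** 110 × 0.50 × 0.90 = 49.5, rounded to 50. The largest exact (Clopper-Pearson) 90% interval width at n = 50 is 0.248, within the stated 0.25.

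**Step 2: set restricted to BRAF-mutated patients under the status rule.** Tissue-tested mutants enter whatever their blood result: 49.5t. Untested mutants enter only if blood-positive: 49.5(1 − t)q.

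- Set size = 49.5 × [t + (1 − t)q]. Example: 49.5 × (0.5 + 0.5 × 0.3) = 32.2. Over the range: 21.8 (t = 0.3, q = 0.2) to 42.1 (t = 0.7, q = 0.5).
- Reported positivity = q / [t + (1 − t)q]. Example: 0.3 / 0.65 = 0.46. Over the range: 0.2 / 0.76 = 0.26 to 0.5 / 0.65 = 0.77.
- Assay-negatives = 49.5t(1 − q). Example: 17.3, all of them tissue-tested patients.

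**Step 3: set restricted to tissue-confirmed mutants.** n = 49.5t, which is 14.9 at t = 0.3, 24.8 at t = 0.5 and 34.7 at t = 0.7. Positivity is unbiased for this subgroup.

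**Step 4: all patients with follow-up.** n = 110 × 0.90 = 99. Positivity among all patients is 0.5q (0.15 in the example). With s the assay's sensitivity in mutated patients, the wild-type share of assay-negatives is 49.5 / (99 − 49.5s): 0.56 at s = 0.2 and 0.91 at s = 0.9.

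| Set | n | Positivity reported in the example | Largest exact 90% width |
|---|---|---|---|
| As stated in the plan | 50 | – | 0.248 |
| Mutated by the status rule | 22–42 (example 32) | 0.46 | 0.38–0.27 |
| Tissue-confirmed mutants | 15–35 (example 25) | 0.30 | 0.46–0.30 |
| All with follow-up | 99 | 0.15 | 0.174 |

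Only full tissue coverage (t = 1) would deliver 50 independently identified mutated patients, and the plan says coverage is partial.

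**Step 5: the three-month test.** The plan's 50 × 0.89 = 44.5 gives its 45 patients and a detectable difference of 0.41 SD. From 99 patients, 99 × 0.89 = 88. Square-root scaling gives about 0.41 × √(45/88) = 0.29 SD. This is approximate, and it presumes a usable fold-change in each patient. The plan itself anticipates undetectable earlier results, and an undetectable baseline gives no ratio, so the real number depends on the set chosen.

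**The case against.** The strongest reply is that the plan never says non-mutated patients are left out. Secondary Objective 2 bases the investigation on the Stage II/resected Stage III cohort, the descriptive summaries refer to the whole cohort, the primary Cox models use aggregated data, and the four-group analysis needs tissue-negative patients. The status sentence can be read as a labelling rule: everyone gets a blood status, and some also get a tissue status. Read that way nothing is circular, and outcome by blood result in all such patients is a legitimate prognostic question that matches the secondary objective in section 1. The stated maximum width of 0.25 would also remain true, since 99 patients give 0.174. The plan calls the cohort exploratory and admits: "We cannot predict the sensitivity and specificity of the assay in patients with Stage II or resected Stage III disease".

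Most of this stands, and it rules out three stronger inferences a reader might draw.

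- *That the prognostic analysis is circular as written.* Circularity of the positivity rate arises only if the set is restricted to mutated patients, which no section states outright. For relapse and survival the problem under that restriction is selection on the exposure, because the outcome does not depend on the assay.
- *That AJCC strata without tissue contain only assay-positive patients and add nothing to the stratified tests.* That depends on how finely stage is divided, which the plan does not say. With strata of II versus III, T4 and macroscopic-node patients could supply negatives in each.
- *That only tissue-confirmed carriers can answer the question.* The stated objective is not limited to carriers.

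What the reply does not rescue is the 50. It is derived explicitly from mutated patients and then used as the denominator. Under the whole-cohort reading that number and its basis are wrong.

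**Conclusion.** The concern holds as a mismatch between the stated sample and any set the design can assemble. Under the assumptions above, the 50 becomes about 22–42 with inflated positivity (set defined by the status rule), about 15–35 (tissue-confirmed), or about 99 (everyone with follow-up). The whole-cohort reading fits the rest of the text best and is free of circularity. Its limit is interpretive: with roughly 56–91% of assay-negatives wild-type, the hazard ratio mixes tumour genotype with residual disease, and the listed Cox covariates (age, primary site, sex, LDH) do not include tissue genotype.

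The inflation figures (0.46 for 0.30; 0.26–0.77 over the range) illustrate what happens if the restricted set is used. They do not predict this trial's result, since tissue share and post-resection positivity are not in the documents. Given the exploratory status of the cohort, this is a correction that should be made, not a threat to the trial's primary objective.

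**What to change.** In section 9.1, Secondary Objective 2:

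1. State that the blood-assay result is never a criterion for entering an analysis set.
2. Run the primary positivity, Kaplan-Meier and Cox analyses on all Stage II/resected Stage III patients with a post-resection sample and follow-up. Replace the sample of 50 and the 0.25 width with the values for that set (about 99 and 0.17, if 90% follow-up applies to all).
3. Redo the three-month calculation for the set actually used, saying how undetectable baselines are handled.
4. Add a named supporting analysis among tissue-confirmed mutants: positivity and the assay-positive versus assay-negative contrast, with expected n and width (about 15–35 and 0.46–0.30 if 30–70% have tissue). Keep it alongside the existing four-group analysis.

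Making tissue-confirmed mutants the sole primary set is not recommended. It would confine the result to the tissue-tested patients, chiefly T4 and macroscopic-node disease, and leave few patients for a stage-stratified model with four covariates plus the assay.

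The cost is a change of wording and slightly more analysis, with no new patients or procedures. The tissue-confirmed result will be imprecise and will not apply to patients without tissue.

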### Prognostic Ability of the Assay

Baseline assay results will be categorized as positive or negative and also be described on a continuous scale. The proportion of patients with a positive baseline assay will be presented with a 90% exact binomial confidence interval. Based on a cohort size of 50, the confidence interval will be no wider than 0.25. Confidence intervals will also be presented for the subgroups of patients with intermediate- or high-risk disease. We will also summarize continuous baseline assay levels using descriptive statistics for the complete cohort and according to subgroups.

Preliminary assessments of prognostic ability will be conducted using Kaplan-Meier (K-M) product-limit estimates for relapse or survival and stratified log-rank tests. K-M estimates will be stratified by AJCC stage and assay results to explore assay performance across different prognostic groups. Relapse-free survival and overall survival estimates at pre-specified time points will be presented with 90% confidence intervals estimated using log(-log(survival)) methodology. A secondary analysis will be conducted in the cohort with blood- and tissue-based assessments according to the four groups defined by their combined positive/negative status to look for differences in prognosis.

The relative effect of the blood-based assay with respect to relapse or survival will be estimated using Cox regression models. Since the AJCC staging incorporates prognostic factors such as number of involved nodes, tumor burden, ulceration, and tumor thickness, the Cox models will be stratified by AJCC stage to allow for differences in the baseline hazard of relapse or death. Models will include as covariates age, site of the primary melanoma, sex, and baseline serum LDH in addition to the blood-assay results. We will use aggregated data for the primary models; secondary models will be fit separately for the intermediate- and higher-risk cohorts. Hazard ratios for the assay will be presented with 90% confidence intervals.

### Predictive Ability of the Assay

The behavior of the blood-based assay over time will be summarized graphically by AJCC stage or according to melanoma treatment. The status of the assay will be shown at each assessment time for each patient, in addition to time of disease progression. Of particular note will be assessment times where a previously undetectable assay becomes detectable, or times where there is a doubling in the assay relative to baseline. Treatment will be classified into four groups: immunotherapy, BRAF/MEK inhibitors, other translational signal transduction/targeted therapies, or chemotherapy (cytotoxic therapy).

The first assessment of assay performance over time will take place at 3 months and will be based on fold-changes in the quantified assay relative to baseline. This early look will minimize the number of patients lost due to rapid progression of disease. Based on 18-month progression rates reported in the literature, we estimate that approximately 11% of patients will have progressed by the time of the 3-month assessment. For an initial cohort size of 50 patients, and assuming that 45 patients will have 3-month assay, a Wilcoxon-signed-rank test, comparing the observed fold-change with one, with a two-sided type-I error of 10%, will have 80% power to detect a difference in fold-change that is 0.41 times the standard deviation.

In more exploratory analyses, we will model the behavior of the assay over time using repeated measures, random-effects regression with the continuous assay measure as the dependent variable. Models will include as covariates AJCC stage and treatment classification, in addition to other prognostic factors. To investigate the relationship between the assay and PFS (or OS), we will use the extended Cox (EC) model with assay performance as the time-dependent covariate. Models will be stratified by AJCC stage, and will include treatment group and prognostic factors as predictors. In separate EC models, the assay will be modeled (a) on a continuous scale, (b) based on fold-changes from baseline, and (c) based on an indicator of assay response (double the baseline level or change from non-detectable to detectable).

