## 9. STATISTICAL CONSIDERATIONS

### 9.1 Study Design/Endpoints

**Primary Objective: To determine the sensitivity and specificity of the peripheral blood BRAFV600 mutation detection.**

Two cohorts of melanoma patients will be assessed using the blood-based assay: patients with advanced disease (non-resectable Stage III or Stage IV), and patients with Stage II and resectable Stage III disease. Assessments of diagnostic accuracy, such as sensitivity, specificity, and positive predictive value (PPV) of the blood-based assay, will be compared separately for the two cohorts, and will use paired binary data. Sample size estimates are based on the binomial distribution and joint 90% confidence regions for sensitivity and specificity to adjust for the two comparisons being performed. Positive and negative expression will be determined using optimized cut points for the assay that have already been established.

We are seeking evidence that the assay has the ability to detect both the presence of BRAF mutation in melanoma (sensitivity) and accurately indicate when a BRAF mutation is not present (specificity) in order to provide BRAF-directed therapy when indicated. We propose a sample of 110 patients with advanced melanoma to test the performance of the assay, and would require sensitivity of at least 0.80 and specificity of at least 0.90. We set our target sensitivity to be 0.90 and specificity to 0.95. With a sample size of 110 patients (approximately 55 with BRAF mutation and 55 without) and the assumed target sensitivity, the lower bound of the joint 90% confidence region will be greater than 0.82; the lower bound of the 90% joint confidence region for the specificity will be approximately 0.90.

We will also estimate the PPV of the assay to evaluate the practical utility of the test. Based on a sample size of 110 patients, Table 1 summarizes the estimated PPV and corresponding 90% confidence intervals over a range of prevalence rates of BRAF mutation, using the minimum and target levels of sensitivity and specificity. With a sample of 110 patients, the lower bound of the 90% confidence interval for PPV will be no less than 0.74.

Table 1 – Estimates of PPV and 90% Confidence Intervals

Prevalence Rate	Sensitivity	Specificity	PPV	90% Confidence Interval for PPV
0.4	0.80	0.90	0.84	(0.74 to 0.91)
	0.90	0.95	0.92	(0.83 to 0.97)
0.5	0.80	0.90	0.89	(0.80 to 0.94)

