## Secondary Objectives

### 1. Exploration of the pharmacodynamic effects of MAPK pathway inhibitors on pre- and on-treatment peripheral blood BRAFV600 mutational testing.

The exploration of pharmacodynamic effects will be based on the cohort of patients with advanced, BRAF-mutated disease confirmed by tissue analysis. We would expect that 50% of the cohort would have BRAF-mutated disease and that 90% of those patients will agree to participate in the pharmacodynamic studies. This results in a sample of size 50.

Our first investigation will correlate blood-assay results with pre-treatment radiographic measures of disease burden. We hypothesize that the cases with the lowest tumor burden would be most likely to have a negative blood assay result. We will use the sum of the longest diameter of tumor target lesions as the measure of disease burden using RECIST criteria (version 1.1). For this analysis, tumor burden will be a continuous outcome, and the blood assay will be classified as positive or negative. We will summarize baseline tumor burden descriptively and compare by assay result using the Wilcoxon rank-sum test. If the blood-assay is positive in 80% of the samples (N=40) and negative in 20% (N=10), a Wilcoxon-rank sum test, with a two-sided type-I error of 10%, will have 80% power to detect a difference in disease burden that is 0.95 times the common standard deviation.

The behavior of the blood-based assay with respect to early changes in disease will be assessed at the time of the first restaging. Since there are no prior data to suggest how assay levels will change in response to treatment, analyses will be primarily descriptive. Two analyses are proposed to explore the relationship between the performance of the assay and early clinical response. In both analyses, clinical response will be classified according to RECIST criteria (i.e., CR/PR vs. SD vs. PD vs. not assessable).

At the time of the first restaging, pre- and on-treatment blood-assay levels will be compared. Fold-changes in assay response will be calculated (post/pre). Fold-changes will be used as a continuous measure and will also be classified according to 0.5 or less (assay-based response), 2 or greater (assay-based progression) and between 0.5 and 2 (intermediate). Fold changes in the assay will be compared across RECIST responses using the Kruskal-Wallis test. In addition, for

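### The 3-month signed-rank test compares the raw fold-change with one: if ratios are log-symmetric it exceeds its stated 10% error, and it has no rule for an undetectable baseline

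*Combined protocol and SAP*

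**What the plan says.** In section 9.1, Predictive Ability of the Assay, the first look at change over time in the resected cohort is at 3 months and uses "fold-changes in the quantified assay relative to baseline". The planned test is a Wilcoxon signed-rank test, "comparing the observed fold-change with one, with a two-sided type-I error of 10%, will have 80% power to detect" a difference of 0.41 times the standard deviation. The number analysed comes from an initial 50, "assuming that 45 patients will have 3-month assay"; the only stated loss is about 11% progressing before that visit.

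Fold-change is defined under Secondary Objective 1, for the advanced cohort: "Fold-changes in assay response will be calculated (post/pre"). No log transform of the assay or of the fold-change is stated; in section 9 the word log occurs only in the log-rank test and in the confidence intervals for survival.

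The same subsection expects undetectable results. Its graphics are to highlight times when "a previously undetectable assay becomes detectable", and extended Cox model (c) uses an indicator defined as "double the baseline level or change from non-detectable to detectable".

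**The concern.** There are two gaps in one test.

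**Scale.** The signed-rank test ranks distances from the null value, so it holds its level only if those distances are symmetric about that value. A ratio is bounded below by 0 and unbounded above. If baseline and 3-month levels are exchangeable when nothing has changed, post/pre and pre/post have the same distribution. That is symmetry of the log ratio about 0, not of the ratio about 1. The test would then report a rise too often under no change, and would be weaker for a true fall than for an equal rise.

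**Undetectable baseline.** The ratio has no value when the baseline is recorded as undetectable. The patients the plan most wants to notice, those who turn detectable, have no defined place in the one powered test of change over time in this cohort. Whether to drop, floor or otherwise score them would be decided after the data are seen.

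**Working it through.** **Inputs from section 9.1.** n = 45; two-sided alpha 0.10; effect 0.41 SD; stated power 80%. The 50 is 110 × 0.5 × 0.9 = 49.5 (expected BRAF-mutated disease and available follow-up); the 45 is 50 × 0.89 = 44.5. Neither step allows for undetectable baselines.

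**Step 1: the plan's own power.** No method is named. I used a two-sided one-sample noncentral t with n multiplied by the asymptotic relative efficiency (ARE) of the signed-rank test and noncentrality 0.41 × √(n × ARE).
- ARE 0.864 (worst case): 45 × 0.864 = 38.88, power 0.807.
- ARE 3/π = 0.955 (normal data): power 0.841.

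The stated 80% is reproduced with the worst-case efficiency, provided the data are symmetric about their centre. It is not an arithmetic error.

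**Step 2: how the raw scale ranks equal changes.** A halving gives |0.5 − 1| = 0.5; a doubling gives |2 − 1| = 1. The doubling gets the higher rank. On the log scale both distances are 0.693, and they tie.

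**Step 3: error rate under no change.** Assumption: log fold-change is normal with mean 0 and SD s (natural log), with s chosen over a range because the documents give none. 100,000 simulated trials per setting, n = 45, normal-approximation signed-rank test at two-sided 10%:

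| s | Raw scale, total error | of which false rises | Log scale, total error |
|---|---|---|---|
| 0.1 | 10.3% | 6.7% | about 10% |
| 0.25 | 12.6% | 10.3% | about 10% |
| 0.5 | 18.5% | 17.4% | about 10% |
| 1.0 | 33.3% | 33.0% | about 10% |

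At s = 0.693, where one SD is a doubling, the raw-scale error is 24.2%. If fold-changes were symmetric about 1 on the raw scale, the test would hold its 10%.

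**Step 4: power for a true log-scale shift of 0.41 SD.**

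| s | Raw scale, rise | Raw scale, fall | Log scale, either direction |
|---|---|---|---|
| 0.1 | 88% | 80% | 84% |
| 0.25 | 92% | 72% | 84% |
| 0.5 | 95% | 58% | 84% |
| 1.0 | 98% | 37% | 84% |

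**Step 5: fewer usable ratios.** The share of undetectable baselines is not given, so the counts below are assumptions. The formula is that of Step 1.

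| Informative ratios | Power, ARE 0.864 | Power, normal log ratios |
|---|---|---|
| 45 | 81% | 84% |
| 40 | 76% | 80% |
| 36 (20% lost) | 72% | 76% |
| 22 (about half lost) | 53% | 57% |

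**Step 6: does a floor work?** Pairs were simulated as exchangeable under no change and left-censored at a detection limit, with 80% or 50% of values detectable and log-ratio SD 1.0 or 0.5. Pairs undetectable at both times were discarded as zero differences. The two-sided error stayed at 9.8–10.4% with the floor at the limit, half of it or a tenth of it. Power for a given shift varied by at most about 4 points between floors.

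**The case against.** The strongest reply is that the size of the scale problem is wholly assumed. No section gives an SD or distribution for the fold-change, and at log-SD 0.1 the error is 10.3%, which nobody would mind. This stands: what is shown is a conditional risk.

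Second, the plan does not say that the ratio is untransformed. A null of one for the ratio is a null of zero for its log, and the 0.5 and 2 cut points in the advanced cohort are reciprocal. But the sentence tests the observed fold-change, sizes the effect in SDs of the fold-change and mentions no log, so the raw reading is the natural one.

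Third, undetectable baselines may be few, because "Positive and negative expression will be determined using optimized cut points for the assay", applied to a densitometry signal, and a sample below a cut point may still have a measurable level. Converters are also not ignored: they appear in the graphics and in Cox model (c), and they can enter the "random-effects regression with the continuous assay measure as the dependent variable" and Cox model (a). All true, but the signed-rank test itself still has no rule. Cox model (b), which uses fold-changes, has the same gap.

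Fourth, a floor does not make rises and falls exactly equal in power. With between-patient log-SD 1.0, log-ratio SD 1.0 and the floor at the limit, power for a 0.41 SD shift is about 81% for a rise and 79% for a fall with 80% detectable, and about 71% and 64% with 50% detectable. This is a real limitation, but far smaller than the raw-scale gap at the same log-ratio SD (98% against 37%, without censoring).

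Finally, this is one secondary test in a cohort the plan calls exploratory. That limits its weight, but the plan still attaches an error rate and a power to it.

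**Conclusion.** The concern holds. If ratios are log-symmetric under no change, the test as written does not keep its 10% error: the excess runs from negligible (10.3% at log-SD 0.1) to large (18.5% at 0.5, 33.3% at 1.0), almost all of it false rises, with a matching loss of power for falls. The actual size cannot be determined from the documents. Separately, the test has no rule for an undetectable baseline, and the 80% power applies only if all 45 ratios are usable.

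The stated power is otherwise reproducible and the sample size need not change: on the log scale, 45 informative ratios give 84% power with normal log ratios and 81% at worst-case efficiency. The primary endpoint is untouched. This should be changed because the remedy is cheap; confidence is medium because the SD and the number of undetectable baselines are unknown.

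**What to change.** In section 9.1, Predictive Ability of the Assay:

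1. Test log(post/pre) against 0 by the signed-rank test and express the 0.41 SD effect on the log scale.
2. Pre-specify a floor for undetectable values (for example the detection limit), applied at both baseline and 3 months, so that undetectable-to-detectable counts as a rise and the reverse as a fall.
3. State that patients undetectable at both times are zero differences that add no information, and report how many there are.
4. State the power as conditional on the number of informative ratios, for example with the figures for 45, 40, 36 and 22.
5. Preferably give one definition of fold-change for all of section 9, so that Cox model (b) and the advanced-cohort fold-changes follow the same rule.

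The cost is SAP wording and a little programming; no new samples or visits. The downside is that the chosen floor sets the weight given to converters and so affects power (by at most about 4 points between the floors tried) and leaves a small rise/fall difference. It does not affect the error rate when changes in either direction are equally likely.
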